Exclusion Criteria:	
Exclusions:
 
 • Children with more than two prior admissions to hospital with severe LRI as defined by study eligibility criteria • Prematurity <32 weeks gestation • Children with a diagnosis of chronic lung disease • Children known to have chronic health problems of clinical significance affecting daily life: 
 ○ cardiovascular ○ neurological ○ immunodeficiency ○ multiple congenital abnormalities ○ enteral feeding
Intervention:	
The intervention programme is based on the CF model of care for early childhood with regular clinic review for any deviation from normal health and to institute early treatment and/or preventative care. Reviews will be undertaken as a minimum at ,1, 4.5, 8, 12, 15, 18, 22 and 24 months after the day 0 assessment and as required in one of four community centres (Otaru, Mangere, Manurewa, Pukekohe) staffed by the nominated general practitioner (GP) or nurse practitioner and practice nurse. Any child with ongoing respiratory problems will be referred to the Paediatrician clinic for further management and immediate discussion/transfer to paediatric respiratory specialist care as needed. Co-ordination will be undertaken by the study respiratory nurse who will attend all clinics and will undertake follow up in the community of any non-attenders.

Control:	
The families will receive the current 'usual care' which is GP review for family directed health concerns with re-referral to paediatric services as necessary. These families will be followed up with a three monthly phone call to ensure contact details are maintained, a home visit prior to the 24 month clinic may be necessary if phone contact is unsuccessful.

Duration of Treatment:	
24 month follow-up is required for participants in both study groups.

Assessments / Study Procedures	
See the attached Schedule of Assessments for details of the assessments to be conducted at each study visit.

Study Endpoints: Primary:	
Evidence of respiratory morbidity at 24 month follow up during a time of stability, as assessed by:
 
 • Abnormal CXR Brasfield score of $\leq 22/25$ ($25/25$ = normal). • And/or abnormal clinical examination (defined as clubbing and/or MCIC and/or crackles on auscultation).
Secondary:	
 • Readmissions with LRI, medically attended LRI/wheezing episodes/asthma diagnosis • All CXR changes

[figure not shown]
- Bx on HRCT if indicated
- Nasal swab/sputum cultures
- Estimation of direct health costs of intervention
- CMC on history (defined as daily moist cough for >3 months or 3 or more episodes of moist cough for > 1 month).

Health Economic Sub-study: 95% confidence intervals for incremental cost-effectiveness ratios and cost-effectiveness acceptability curves will be calculated for endpoints to compare the intervention with usual care. Only direct costs of health care will be included.

Statistical Methods: **Sample Size Determinations:** 400 children will be randomised 1:1 to intervention and control groups. Assuming 80% retention, 160 per group will be available at 2 year follow up. Note that this retention has been demonstrated in our previous SA studies^{33,42}. With this sample size and assuming 40% of the controls have chronic respiratory symptoms (less than seen in the one year follow up study) there will be 91% power to detect a 50% reduction at the 1% level of significance (i.e. 20% of the intervention group having chronic respiratory symptoms). There will be 80% power to detect 45% reduction, at the 1% level. Should the rate in the control group only be 30%, there will still be 90% power to detect a 50% reduction at the 5% level of significance. The SA area includes 113,000 children < 15 years of age including 26% Maori and 29% Pacific with 71% of children living in the lowest socioeconomic quintile³⁵

Analysis: The primary hypothesis of a difference in chronic respiratory morbidity at 24 months post index hospital admission between the intervention and control groups will be tested using logistic regression with chronic respiratory morbidity, present or absent as the outcome and age, ethnicity, deprivation index, and group as explanatory variables. The “intention to treat” population will be used for all those completing the 24 month follow up. A further exploratory analysis will be done including the interactions of the other variables with group to ensure there is no evidence indicating the possibility of a differential effect of the intervention. Other outcomes will be investigated with the same explanatory variables using binary or ordinal logistic regression or linear regression, depending on the distribution of the variable.

Intervention Study of Children at High Risk of Chronic Lung Disease

STUDY PROCEDURES: Schedule of Assessments – Intervention Group

Procedure	Screening and Enrolment	Visit 1 (Month 1) ^b	Visit 2 (Month 4.5) ^b	Visit 3 (Month 8) ^b	Visit 4 (Month 11.5) ^b	Visit 5 (Month 15) ^b	Visit 6 (Month 18.5) ^b	Visit 7 (Month 22) ^b	Final Visit (Month 24)
Medical Assessment	X	X	X	X	X	X	X	X	X
Medical Treatment	X	X	X	X	X	X	X	X	X
Social/Housing Assessment	X	X ^d	X ^d	X ^d	X ^d	X ^d	X ^d	X ^d	
Immunisation		X ^d	X ^d	X ^d	X ^d	X ^d	X ^d	X ^d	
Education		X	X	X	X	X	X	X	
Chest Physiotherapy		X ^d	X ^d	X ^d	X ^d	X ^d	X ^d	X ^d	
Smoking Cessation		X ^d	X ^d	X ^d	X ^d	X ^d	X ^d	X ^d	
Nutritional Assessment		X	X	X	X	X	X	X	X
Dental Review		X	X	X	X	X	X	X	X
Treatment Follow-up		X	X	X	X	X	X	X	
Blood test		X ^a							X ^e
Nasopharyngeal Swab									X ^f
Chest X-ray	X ^a	X ^c	X ^c	X ^c	X ^c	X ^c	X ^c	X ^c	X ^c
Collect GP, ED and hospital visits	X	X	X	X	X	X	X	X	

a. If not already taken as part of routine care while in hospital.

b. If concerns are raised during routine visit child/whanau may be brought back earlier for assessment of intervention effect. This will be decided by attending physician. At anytime discussion with or a referral to the general paediatrician or respiratory paediatrician depending on need can occur.

c. If the child is symptomatic at this visit delay clearance chest x-ray until stable/or clinically indicated – decision by attending physician.

d. As required

e. Blood sample taken for both immediate testing for iron, full blood count and storage for later Vitamin D and IgE testing.

f. Nasopharyngeal Swab sample to be stored for later virus and bacteria testing,

STUDY PROCEDURES: Schedule of Assessments – Non Intervention Group

Procedure	Screening and Enrolment	Visit 1 (Month 1)	Visit 2 (Month 4.5)	Visit 3 (Month 8)	Visit 4 (Month 11.5)	Visit 5 (Month 15)	Visit 6 (Month 18.5)	Visit 7 (Month 22)	Final Visit (Month 24)
Medical Assessment	X								X
Medical Treatment									X
Blood test									X ^e
Nasopharyngeal Swab									X ^f
Chest X-ray									X
Phone contact by CHW and/or Research Nurse		X	X	X	X	X	X	X	
Collect GP, ED and hospital visits	X	X	X	X	X	X	X	X	

e. Blood sample taken for both immediate testing for iron, full blood count and storage for later Vitamin D and IgE testing.

f. Nasopharyngeal Swab sample to be stored for later virus and bacteria testing,

Study Background:

Lower respiratory infection (LRI) is a significant problem for NZ children and the proposed intervention is a programme of change with regular clinical follow-up combining two approaches that have been successful in other areas, firstly early intervention in children with cystic fibrosis (CF) internationally and secondly community based care in adults with chronic lung disease in South Auckland (SA). This type of randomised interventional study has never been previously undertaken. It will provide health benefit whilst determining the feasibility of instituting a new health care delivery model in the community and also collecting informative data for this disadvantaged population within the next five years.

LRI admission for NZ children: The NZ rate of hospital admissions for LRI (predominantly bronchiolitis or pneumonia) from 1996 to 2006 was 10.9/1000 for children <15 years, and for SA was 18.3/1000 - both very high by international standards¹. In the < 2 year age group admissions for LRI are 103/1000 nationally but are again higher in SA at 177/1000. The relative risk of admission for LRI is 1 European, 5.2 Pacific and 2.9 Māori, in addition there was a 4.9 relative risk for those in the lowest socioeconomic quintile. When compared to population studies in the US and UK, this is an increase of 2.5 x overall, 4.5 x for Pacific, 3.5 x for Māori, and 4 x for those in decile 10^{2,3,4,5,6,7}. In 2000-2004 respiratory diseases in Māori children were the first to third most common reason for admission to hospital in the age groups <1 year age, 1-4 years age, 5-14 years age, 15-24 years age⁸. Admission rates for LRI in the early age groups are also increasing over time and increasing in severity i.e. not associated with an increased admission of less severe disease. Bronchiolitis admissions increased 118% over a decade (1988-1998), accompanied by an increase in severity; from 25% requiring any support to 59% requiring oxygen, 21% nasogastric fluids, 22% intravenous fluids, 8% admitted with apnoea and 3.1% requiring ventilation⁹. Pneumonia also had an annual increase of 5% over 7 years (to 1995) with increased severity and again admissions were skewed towards the younger age group¹⁰. In the Pacific Island Family Study following 1398 children has shown that breathing problems (cough and wheeze) are the most frequent symptoms complained of by Pacific parents^{11,12}. Elliot et al in 1971 surveyed 2143 pre-school Rarotongan children performing a chest x-ray (CXR) on every third child with abnormalities seen in 37% and peak age of abnormality 24 months¹³.

Progression from LRI to Chronic moist cough (CMC), Chronic suppurative lung disease (CSLD) and Bronchiectasis (Bx): While the exact pathway from LRI to persistent and chronic respiratory symptoms and ultimately irreversible lung disease is not yet understood, cohort studies of Alaskan and Australian Aboriginal children have clearly demonstrated that early admission to hospital with severe LRI is strongly linked to later development of CSLD/Bx^{14,15}. A follow-up study of Alaskan children subsequent to hospital admission with RSV bronchiolitis or pneumonia < 3 years age demonstrated 46% with productive cough, 22% with chronic bronchitis and 10% with Bx at age 5 years. The relative risks were 3.9 if their CXR had shown parenchymal densities and 3.0 if there were persistent parenchymal densities for greater than 6 months. A case control study of Aboriginal children in Australia demonstrated that a history of hospitalised pneumonia gave an odds ratio of 15.2 for developing Bx. Two studies have described the high rates of Bx in NZ children with 80% being Māori and/or Pacifica^{16,17}. A prospective national surveillance study for all new cases diagnosed in 2001-2003 describe an incidence of 3.7 per 100,000 which is 3-18 times higher than described in other western countries^{18,19}. If all the children live to 15 years, this gives a prevalence of 1 in 3,000 overall, but 1 in 1700 in Māori and 1 in 650 in Pacifica. This means that the incidence in Pacifica is four times more common than CF in the general NZ population. The disease is more severe in our population than any other populations described with 81% bilateral disease and 64% having 4 or more lobes involved²⁰. Ethnicity and deprivation are also strongly linked to morbidity and premature mortality for Bx in the SA adult population^{21,22}. In both our NZ paediatric studies, the first hospital admission for respiratory disease had occurred 4 years prior, and mean duration of CMC 2 years prior to the

diagnosis^{16,17,20}. Despite extensive investigation only 10% had a specific underlying immune problem, again a smaller percentage than any other population described. It is therefore increasingly realised that a proportion of children progress from early, severe LRI to CMC, CSLD and/or Bx^{23,24,25}. While we currently have trials of management underway to treat children with Bx, prevention of irreversible disease should be possible^{26,27}. This has been the subject of a recent Thoracic Society of Australia and New Zealand task force in 2009 with the recommendations to be published²⁸.

Cystic Fibrosis Model of Care: CF is a genetically determined disease seen predominantly in European populations which also results in repeated and progressive lung disease. An increasing life expectancy with reduced respiratory and nutritional morbidity has already been achieved in children with CF using a clinical model of care with regular review from infancy, early detection of deviation from normal health and early intervention to prevent ongoing disease this has now been published as “Standards of Care”^{29,30,31,32}. Leading research groups (NZ, Australia, Alaska, UK)^{24,26,27} have recommended a CF style approach for non-CF Bx, but this is already too late to prevent the actual disease. *We believe that by commencing this early intervention programme when the risk factors for developing the disease rather than the disease itself appears we will prevent respiratory morbidity and irreversible disease.* This also requires taking the model outside of the specialised hospital clinics in which it is currently practised and basing it in the community^{29,30}. We have the at risk population within a geographically constrained area, with known high end-disease prevalence of greater severity than those in other areas (suggesting under-estimation), and the connected multi-disciplinary team with which to conduct this research. This has been confirmed by our pilot study.

LRI follow up study of SA children: We conducted a prospective epidemiology study of LRI in children hospitalised in SA from August to December 2007 and found that 223 of 489 had a discharge diagnosis of pneumonia or severe bronchiolitis as defined for this application³³. These were approached in order of enrolment for one year follow up. The first 130 were contacted and 94 (with a demographic profile the same as the study group overall) were able to be seen with a clinical review, examination, questionnaire and CXR. We found 50% had a significantly abnormal CXR, 30% had CMC and 30% had moist cough in clinic (MCIC) with only 20% well. In summary two thirds had evidence of continuing respiratory morbidity with one or more of these abnormalities 12 months after the index event of hospital admission even when reviewed at a time of stability.

Study Timelines

This study has a 24 month follow-up for all children enrolled. Allowing for recruitment of suitable participants the study is due to proceed for 48 months.

Study Sites

This study will be conducted at four community centres in the Counties-Manukau catchment area – Otara, Mangere, Manurewa and Pukekohe.

Research activities will be centrally coordinated by the study team at Kidz First Childrens Hospital.

Ethical Requirements and Annual Reporting

Ethical approval has been received from Northern X regional ethics committee (reference NTX/10/09/094) An annual report will be provided to the ethics committee and the Health Research Council.

Adverse Events and Serious Adverse Events

As this study is assessing two methods of providing care rather than specific drug interventions we do not envisage the programme will create adverse or serious adverse events however, all adverse experiences either observed by the investigator or one study staff, or reported by the patient's parents/guardians spontaneously or in response to a direct question, that occur during the study period or a need for a change in therapy, will be evaluated by the investigator and noted in the study file. Events after the study period also thought to be due to a study intervention will be included.

A serious adverse event (SAE) is generally defined as any event that is fatal, life-threatening, permanently disabling, incapacitating or results in hospitalisation, prolongs a hospital stay or is associated with congenital abnormality, carcinoma or overdose.

Serious adverse events:

For this trial, serious adverse events are the following:

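### The primary population is called intention to treat but is limited to children completing the 24 month visit, so it is an available-case analysis with about 80 of 400 randomised children expected to be absent

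*Protocol*

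**What the plan says.** The Analysis paragraph under Statistical Methods in the Protocol Synopsis names an intention-to-treat population and says that this "population will be used for all those completing the 24 month follow up". The primary test is a logistic regression of chronic respiratory morbidity on group, age, ethnicity and deprivation index.

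The sample size paragraph states "400 children will be randomised 1:1 to intervention and control groups" and "Assuming 80% retention, 160 per group will be available at 2 year follow up".

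The primary endpoint (chest X-ray score and/or clinical examination) is assessed at the 24 month follow-up. A child who is not seen then has no primary outcome.

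Contact differs by arm. Under Intervention, the child has scheduled clinic reviews and the study nurse "will undertake follow up in the community of any non-attenders". Under Control, families receive a "three monthly phone call to ensure contact details are maintained", and a home visit before the 24 month clinic is possible if phoning fails. The Schedules of Assessments show seven interim clinic visits for the intervention arm and phone contact at the same seven time points for controls. GP, ED and hospital visits are collected at each of those points in both arms.

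**The concern.** Intention to treat normally means every randomised child, analysed in the arm assigned. Completing the 24 month visit happens after randomisation, so selecting on it can undo the balance that randomisation gave. A report that keeps the label would tell readers that this protection is in place when it is not.

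The intervention is itself a programme of contact, and tracing is organised differently in each arm. It is plausible that different kinds of children are lost from each. Well control children might not return, for example, or unwell children in mobile families might be kept in one arm and lost in the other. The trial's single primary conclusion would then rest on a comparison biased by an unknown amount.

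**Working it through.** **Inputs from the protocol.** 400 randomised 1:1; 80% retention; control rate 40% ("assuming 40% of the controls have chronic respiratory symptoms"); 50% reduction; 1% level.

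**Expected absence.** 400 × 0.80 = 320 completers, 160 per arm. 400 − 320 = 80 children absent, which is 20%.

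**The plan's own power figure.** The protocol says "there will be 91% power to detect a 50% reduction at the 1% level of significance". Two-sided test, pooled variance, n = 160 per arm, 40% v 20%:
- null SE = √(0.30 × 0.70 × 2/160) = 0.0512
- alternative SE = √((0.24 + 0.16)/160) = 0.0500
- power = Φ((0.20 − 2.576 × 0.0512)/0.0500) = Φ(1.36) = 91.3%

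This reproduces the stated 91%. The second statement, "There will be 80% power to detect 45% reduction, at the 1% level" (40% v 22%), gives 82.2% without and 78.8% with a continuity correction, either side of the stated figure. The design is sized on completers, so power already allows for the loss. The question is bias and labelling.

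**Illustration 1: unequal retention (assumed).** Let p be the true rate in both arms, r the retention and m the rate among non-attenders. The rate seen in completers is

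q = (p − (1 − r)m)/r

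Take p = 35%, which lies between the protocol's 30% and 40% control rates, and m = 20%. With 90% intervention and 70% control retention:
- intervention: (0.35 − 0.10 × 0.20)/0.90 = 36.7%
- control: (0.35 − 0.30 × 0.20)/0.70 = 41.4%
- spurious difference d = 0.0476, with n = 180 v 140
- pooled rate 0.3875; null SE 0.0549; alternative SE 0.0550
- rejection probability = Φ((0.0476 − 1.96 × 0.0549)/0.0550) + Φ((−0.0476 − 1.96 × 0.0549)/0.0550) = 0.138 + 0.002 = 14%

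The retention gap drives the result, so it has to be varied (m = 20% throughout):

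| Retention, intervention/control | Completers, intervention v control | Difference (points) | Type I error at nominal 5% |
|---|---|---|---|
| 80%/80% | 38.8% v 38.8% | 0 | 5.0% |
| 82.5%/77.5% | 38.2% v 39.4% | 1.2 | 5.5% |
| 85%/75% | 37.6% v 40.0% | 2.4 | 7.2% |
| 90%/70% | 36.7% v 41.4% | 4.8 | 14% |

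The non-attender rate matters too. At 90%/70% with m = 30%, the difference is 1.6 points and the error 6.0%. With m = 50%, completers show 33.3% v 28.6%, which is 4.8 points in the other direction.

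**Illustration 2: equal retention, different reasons for loss (assumed).** Take a true rate of 40% in both arms. Controls are retained at 87.5% if ill and 75% if well, so overall 0.4 × 0.875 + 0.6 × 0.75 = 80%. Intervention retention is 80% regardless of outcome. Completers show 0.35/0.80 = 43.8% of controls v 40.0% of the intervention arm. Type I error is about 10.4% at nominal 5%. Equal retention alone is therefore no guarantee.

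**Illustration 3: sensitivity of the planned result.** If completers show the planned rates (64/160 v 32/160), z = 3.90 and p = 0.0001. Filling in the 40 absent children per arm with assumed rates:

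| Absent children, control/intervention | All 400, control v intervention | p |
|---|---|---|
| 40%/40% | 40% v 24% | 0.0006 |
| 20%/40% | 36% v 24% | 0.009 |
| 40%/60% | 40% v 28% | 0.011 |
| 20%/60% | 36% v 28% | 0.086 |

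These are pooled z tests on completed counts. They ignore imputation uncertainty and show direction and scale only.

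**The case against.** Four objections carry weight.

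1. **The natural reading is benign.** The sentence probably means that children are analysed in their assigned arm wherever the outcome exists. Nothing excludes a child who has outcome data, or excludes for non-adherence. That stands, but the set so described is still available case, and the label remains wrong.

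2. **Missing-data methods belong to the SAP.** Agreed. Their absence from the protocol is not the point. The point is the population that the protocol itself fixes for the primary test.

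3. **The model gives some protection.** When only the outcome is missing, logistic regression on completers is valid if loss depends only on arm, age, ethnicity and deprivation. Unequal retention by itself therefore does no harm. Protection fails only if, given those variables, loss still relates to the child's respiratory outcome and does so differently by arm.

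4. **The tracing contrast can be overdrawn.** Controls are contacted by a community health worker and/or research nurse at the same seven time points, with a home visit as a fallback, and the protocol expects 160 per group.

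A reader might infer that the plan sets out to discard 20% of children. It does not: 20% is anticipated loss used for sizing. A reader might also infer that the programme is known to change completion, or that 14% is the expected false-positive rate. The protocol shows no effect of arm on completion, and 14% needs a 20-point retention gap that it does not give.

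**Conclusion.** The point holds as one about labelling and an unexamined assumption. The protocol states an available-case population under an intention-to-treat name, with about 80 of 400 randomised children expected to be absent. Differential contact makes outcome-related loss that differs by arm plausible. It does not establish it, and neither the size nor the direction of any bias can be read from the documents.

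Under the assumptions of Illustration 1 with non-attenders at 20%, type I error at nominal 5% runs from 5.0% (equal retention, same non-attender rate in both arms) to 14% (90%/70%). These are crude rates without the planned covariate adjustment. Every retention gap and non-attender rate used is an assumption. Power is not in question.

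It would also be too strong to say that imputing all 400 outcomes cures the problem. Imputation assumes data missing at random, so it removes outcome-dependent loss only as far as the recorded variables explain it. A Month 24 examination and X-ray result cannot sensibly be imputed for a child who has died.

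**What to change.** - Define intention to treat as all randomised children in their assigned arm.
- Name the completer logistic regression available case, and state that it assumes outcomes are missing at random given its covariates.
- Add an all-randomised analysis by multiple imputation within arm, using baseline covariates, index severity and the GP, ED and hospital visits already collected in both arms.
- Add a delta (tipping-point) analysis that varies the missing-outcome rate separately by arm, because imputation alone does not remove outcome-dependent loss.
- Report deaths separately by arm, and do not impute a Month 24 outcome for them.
- Report retention by arm.

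The cost is protocol and SAP wording and a few days of analysis, with no new patients or data. The downside is that the conclusion may have to be stated more cautiously.
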